**Study Design**

Describe and explain the study design (e.g., observational, secondary analysis, single/double blind, parallel, crossover, deception, etc.).

- *Clinical Research:* Indicate whether subjects will be randomized and whether subjects will receive any placebo.
- *Community-Based Participatory Research:* If you are conducting [community-based participatory research \(CBPR\)](#), describe strategies for involvement of community members in the design and implementation of the study, and dissemination of results from the study.
- *Qualitative research:* Indicate ranges where flexibility is needed, if a fixed interview transcript is not available, describe interview topics including the most sensitive potential questions.
- *Research Repositories:* If the purpose of this submission is to establish a Research Repository (bank, registry) and the material you plan to collect is already available from a commercial supplier, clinical lab, or established IRB approved research repository, provide scientific justification for establishing an additional repository collecting duplicate material. Describe the repository design and operating procedures. For relevant information to include, see the [UK Research Biospecimen Bank Guidance](#) or the [UK Research Registry Guidance](#).

We will perform a stratified cluster randomized controlled trial with randomization of participating clusters into a "GROUP CARE" or "TELEMEDICINE" arm. Sites will be stratified into "high volume" (>500 deliveries/year) and "low volume" (<500 deliveries/year). Randomization will be 1:1 within each strata. According to 2016 site specific delivery data, 6 sites are "low volume" and 6 sites are "high volume". All enrolled study patients will continue to receive regular prenatal care (PNC) through their community based obstetric

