## 6 months Post-Partum

- 1) WHO QoL-BRF
- 2) Experience of Care and Health Outcomes (ECHO) - modified
- 3) Cornell Health Services Index (CHSI)
- 4) Fagerstrom nicotine Dependence
- 5) Edinburgh Depression Scale
- 6) GAD-7
- 7) Ages and Stages

Study participants will be asked to complete surveys in REDCap available on iPads dedicated specifically for this project; however, all participants will have the option to complete hard copies of the surveys if they prefer. Data from surveys completed on iPads will be uploaded directly into REDCap. Devices will be managed by UK Healthcare IT, which already deploys a large number of iPad devices and is very familiar with the security and management requirements of iOS based devices. UK Healthcare IT currently has a management app configured to ensure the security of the devices and to apply sufficient restrictions that the devices cannot be used for unintended purposes. All devices will be stored securely in locked cabinets.

We will be collecting the following maternal data:

1. Prenatal labs
2. Infectious complications
3. MAT program participation rate (by patient)
4. Study program participation rate (e.g. frequency of clinic attendance at telemedicine and/or group sessions);
5. Prenatal care attendance (medical record review).
6. Urine drug screen result on admission to labor and delivery, 3 and 6 months postpartum (obtained from medical records)
7. Smoking status: evaluated through patient interview and Fagerstrom Nicotine Dependence Scale at intake, 3rd trimester, 3 and 6 months postpartum.
8. Addiction severity: DSM-5 Criteria for Opioid Use Disorder at intake
9. Obstetric complications including but not limited to Preterm birth <37 GA, growth restriction (<10%ile), preterm rupture of membranes, preeclampsia, multiple gestation, gestational diabetes, chorioamnionitis, miscarriage, fetal demise, cesarean delivery (medical record review)
10. Overdose tracking (overdose reversal agent needed, admitted to hospital/ED for overdose): patient interview at every visit
11. Health services utilization: Cornell Health Service Index administered in 3rd trimester, 3 and 6 months post-partum
12. Patient experience of care: Experience of Care and Health Outcomes (modified) Survey administered in 3rd trimester, 3 and 6 months post-partum
13. Depression: Edinburgh Postpartum Depression Scale administered at intake, 3rd trimester, 3 and 6 months postpartum

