14. Anxiety: GAD7 administered at intake, 3rd trimester, 3 and 6 months postpartum
15. Quality of life: WHO QoL-BRF administered in 3rd trimester, 3 and 6 months post-partum
16. Mother-Infant dyad status/Foster care requirement: retention of custody evaluated by patient interview at hospital discharge, 3 and 6 months postpartum
17. Maternal breastfeeding status: evaluated by patient interview at delivery, 3 and 6 months postpartum.

We will be collecting the following fetal data:

Fetal size per gestational age; Any genetic or structural anomalies; any other fetal complications.

We will be collecting the following neonatal data, including the following assessments:

Gestational age and weight at birth; 5 & 10min Apgar score; NICU/nursery hospital admission; NAS diagnosis & treatment requirement (primary outcome); NAS medication days; in-hospital growth (birth to discharge per day); other infant morbidities; total hospitalization length of stay; immunization compliance, ED visits, follow up with scheduled pediatric visits.

Data will be obtained via medical record review, patient interview, physician/staff report, review of state Medicaid data, and hospital discharge data by the study site research staff with the oversight of the UK-study team.

We will perform fidelity monitoring of intervention delivery. Research nurses/facilitators (group arm), providers (telemedicine arm), and all study participants will be asked to complete a fidelity form, similar to an evaluation form, at the end of each educational session. We will evaluate intervention fidelity by comparing provider and participant responses. If any discordance is identified between provider and participant responses for a given topic, additional training related to intervention delivery may be required.

In each arm, patients will be randomly selected to participant in a qualitative interview process at each participating site at the time of the 6 month postpartum follow-up. The interviews will be facilitated by Co-I [name], who has extensive experience using qualitative techniques with substance-involved patients in community based and treatment settings, with the assistance of research coordinators trained in qualitative interviewing techniques. Patients will be offered a fifty dollar stipend for their time to participate in the interview. 3 patients will be randomly selected from each participating site for a total of 33 interviews.

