## **Statistical Analysis Plan NCT03725332**

To begin, continuous variables (gestational age at birth, neonatal weight, infant hospitalization length of stay, etc.) will be summarized with descriptive statistics (n, mean, standard error, first and third quartiles, and minimum and maximum); categorical variables (NAS treatment required, mother-infant dyad status, preterm birth, maternal smoking status, etc.) will be summarized with counts and percentages. To investigate differences in outcomes between treatment arms, a generalized linear mixed model will be performed. Mixed models allow for additional flexibility to control clustering while controlling for covariates such as socioeconomic status, race, age, addiction severity, if needed. Results will be presented with means (standard error) by treatment arm. Note that the primary outcome requires a noninferiority analysis; the secondary outcomes require superiority analysis to identify between-group differences. Mixed model assumptions will be assessed using plots of each outcome, diagnostics, and/or residual plots. If deviations from distributional assumptions are identified, remedial measures will be deployed as needed. In the case that methods assumptions are not satisfied, remedial measures (eg, variable transformations, nonparametric methods) will be employed.

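### The SAP does not say how maternal instruments repeated over three visits enter the mixed model, and its covariates omit the intake score and the randomization stratum

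*Combined protocol and SAP*

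**What the plan says.** The SAP is a single paragraph. On the model it says: "To investigate differences in outcomes between treatment arms, a generalized linear mixed model will be performed". On correlation it says: "Mixed models allow for additional flexibility to control clustering". The same sentence provides for covariates and gives age, race, socioeconomic status and severity of addiction as examples, to be used where needed. Results are to be given as means with standard errors for each arm. For everything but the primary outcome, "the secondary outcomes require superiority analysis to identify between-group differences". The paragraph names no random effects, visit term, within-woman covariance, target time point or use of intake values.

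The protocol's list of maternal data, under Data Collection & Research Materials, repeats six instruments. Three are also taken at intake, for example "Depression: Edinburgh Postpartum Depression Scale administered at intake, 3rd trimester, 3 and 6 months postpartum". Three start later, for example "Quality of life: WHO QoL-BRF administered in 3rd trimester, 3 and 6 months post-partum".

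The Study Design section says "We will perform a stratified cluster randomized controlled trial with randomization of participating clusters". Sites are stratified by yearly deliveries, above or below 500, and "Randomization will be 1:1 within each strata".

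**The concern.** For an instrument measured at several visits, the arm difference is not defined until the plan says which visit, or which average of visits, it refers to. The SAP leaves that choice to the analyst. Three things depend on it.

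- **Number of tests.** One test per instrument or one per visit are both compatible with the text, and no multiplicity rule is given.
- **What is estimated.** The Study Population section allows enrollment up to 32 weeks, and the Payment section places the prenatal data collection at 28 to 32 weeks. A woman who enrolls late can give her third-trimester answers after little or no exposure, so a third-trimester, a 6-month and an averaged contrast answer different questions.
- **Precision and balance.** With about a dozen randomized sites, chance imbalance between arms is likely. The two variables best placed to deal with it, the woman's own intake score and the stratum, are not in the covariate list. An adjustment made only where needed also leaves the choice of covariates until after the data are seen.

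**Working it through.** The documents state no alpha, standard deviation, intraclass correlation, within-woman correlation or retention rate, so there is no plan figure to reproduce. Values for these below are assumptions.

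**1. Visits** (Schedule of Study Assessments and the maternal data list)

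| Instrument | Intake | 3rd trimester | 3 months | 6 months |
|---|---|---|---|---|
| Edinburgh, GAD-7, Fagerstrom | yes | yes | yes | yes |
| WHO QoL-BRF, ECHO (modified), Cornell index | no | yes | yes | yes |

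**2. Tests.** Post-intake tests by visit: 6 × 3 = 18. One per instrument: 6. At an assumed two-sided 0.05 and independent tests, the chance of at least one false positive is 1 − 0.95^6 = 26.5% or 1 − 0.95^18 = 60.3%. Correlated tests give lower figures.

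**3. Intake as an outcome visit.** If all four visits of the Edinburgh, GAD-7 or Fagerstrom scale were averaged as outcomes, a constant post-intake effect would shrink to 3/4 of its size, because intake precedes the intervention.

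**4. Gain from intake adjustment.** Inputs: 12 equal sites (the Study Population section lists twelve; Research Procedures and Resources say 11), 22 women each (264, against a stated maximum of 267), outcome variance 1. Let c be the site intraclass correlation, r the correlation between a woman's intake and 6-month scores (site included), and b = (r − c)/(1 − c). Assume that the site effect is the same at intake and 6 months. The variance of a site mean is then

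- unadjusted: U = c + (1 − c)/22
- adjusted: A = c(1 − b)² + (1 − c)(1 − b²)/22

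The standard error of the arm difference, with six sites per arm, is √(U/3) or √(A/3), so the relative reduction is 1 − √(A/U).

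- c = 0, r = 0.4: U = 0.0455, A = 0.84/22 = 0.0382, reduction 8.3%.
- c = 0.05, r = 0.6: b = 0.55/0.95 = 0.579; U = 0.05 + 0.0432 = 0.0932; A = 0.05 × 0.177 + 0.95 × 0.665/22 = 0.0089 + 0.0287 = 0.0376; reduction 36.5%.

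| Site correlation c | r = 0.4 | r = 0.5 | r = 0.6 |
|---|---|---|---|
| 0 | 8.3% | 13.4% | 20.0% |
| 0.01 | 12.9% | 18.5% | 25.3% |
| 0.05 | 21.6% | 28.7% | 36.5% |

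Simulation of the fitted mixed model gives about 9 to 38% over the same range.

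**5. Sensitivity to persistence.** If the site effect at 6 months were unrelated to that at intake, the site term becomes c(1 + b²). At c = 0.05, r = 0.5 (b = 0.474): A = 0.05 × 1.224 + 0.95 × 0.776/22 = 0.0612 + 0.0335 = 0.0947, against U = 0.0932. The gain disappears. At c = 0 it stays at 8 to 20%.

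**The case against.** A reader might infer that a model pooling the visits with a site effect alone treats three answers from one woman as three women, so that its standard errors are too small. The documents do not support that. The SAP does not define the level of clustering, so it cannot be said to restrict the model to site. Even if it did, arm is assigned by site, and the arm standard error comes from variation between site means, which already contains the variation between women. At c = 0.01 and r = 0.5 with three visits, the variance of a site mean is 0.01 + 0.49/22 + 0.50/66 = 0.0398, and √(0.0398/3) = 0.1153 is the expected standard error with or without a woman effect. In simulation, the ratio of model to empirical standard error for the site-only model was 0.98 to 1.02, including with unequal sites and with 25% of visits missing.

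A serious understatement arises only if neither effect is fitted. The factor √(1 + 2r) is then 1.34, 1.41 or 1.48 at r = 0.4, 0.5 or 0.6, with a true error of 14%, 17% or 19% for a nominal 5% test before any site effect. Nothing in the SAP suggests that model. The 7 to 8% error that z tests showed with the site-only model comes from having few sites; it falls to about 4 to 6% with a t reference on 10 degrees of freedom, and is a separate matter.

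Three further points are fair. With complete data, a visit-specific contrast from a joint model is essentially the per-visit estimate, so the joint model gains only when visits are missing or an average is the target. The six instruments are listed as maternal data and not named one by one as secondary outcomes, so 18 is an upper count. And the SAP's wording would permit adding the intake score. What remains is that neither that adjustment nor the target visit is fixed in advance.

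**Conclusion.** The point holds as a low-cost improvement; the plan's model is underspecified, not wrong. The visit structure and the target time point are open, and the intake score and volume stratum are missing from the prespecified covariates.

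The gain that can be sized is the 9 to 38% smaller standard error. It applies to the three instruments with an intake score and assumes equal sites. The low end needs only within-woman correlation; the high end also needs a site correlation of 0.05 that persists from intake to 6 months. The benefit of the stratum term was not sized; it aligns the analysis with the randomization.

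A reader might also infer that the trial foresees heavy postpartum loss, or that 6 months is its key visit. The documents give no retention figure and name no key visit for these instruments, so neither inference is part of the point.

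**What to change.** Add to the SAP, for the six repeated instruments:

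- one mixed model fitted to all available post-intake visits, with fixed effects for arm, visit, arm-by-visit and volume stratum, and random effects for site and for woman within site;
- the intake score as a prespecified covariate for the Edinburgh, GAD-7 and Fagerstrom scales, and not as an outcome visit;
- one target visit, or one stated average of visits, per instrument, chosen by the sponsor before analysis. That contrast, with its confidence interval, is the single test for the instrument, and the other visits are supportive.

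Women who miss a visit then still contribute through their other visits, under a missing-at-random assumption.

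The cost is a few lines of SAP text and slightly longer code. All the data are already being collected. The one thing given up is formal testing at the visits not chosen.

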**Objectives**

List your research objectives. Please include a summary of intended research objectives in the box below.

Aim 1.) Conduct a randomized cluster trial using a 'hub and spoke' study design, comparing two delivery modes (local GROUP care vs TELEMEDICINE) for the delivery of a PATHways based patient education curriculum at participating regional sites. Each regional site will be randomized to support one of two study arms: 1) Prenatal group care led by a Perinatal Nurse Facilitator and Peer Support Specialist (GROUP arm); or, 2) Telemedicine consultation provided by a Perinatal nurse educator, substance abuse counselor and/or Peer Support Specialists based at the 'hub' site (TELEMEDICINE arm).

Aim 2.) Evaluate the relative effectiveness of each study arm on primary and secondary maternal and neonatal outcomes as compared to the established PATHways program (UK-PATHways: Hub) at the University of Kentucky.

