## SCHEDULE OF STUDY ASSESSMENTS

## ENROLLMENT/INTAKE

1. DSM-5 Criteria for Opioid Use Disorder
2. Edinburgh Depression Scale
3. Fagerstrom Nicotine Dependence
4. GAD-7 (Anxiety)
5. Adverse Childhood Experience (ACE)
6. Abuse Assessment Screen

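### The SAP leaves covariate adjustment optional and open-ended, and commits neither to the volume stratum used in randomisation nor to the intake scores of scales repeated at follow-up

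*Combined protocol and SAP*

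**What the plan says.** The SAP is a single paragraph. It compares arms with a generalized linear mixed model that accounts for clustering, "controlling for covariates such as socioeconomic status, race, age, addiction severity, if needed". It does not say who judges need, when, or by what rule. It lists no fixed effects beyond the arm comparison and has no separate model for each outcome. Strata and delivery volume do not appear in it.

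The protocol's Study Design section divides sites at 500 deliveries a year, with six sites in each stratum, and states: "Randomization will be 1:1 within each strata".

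Three scales are measured at intake and repeated three times (Data Collection & Research Materials, maternal data items 7, 13 and 14):
- smoking: "evaluated through patient interview and Fagerstrom Nicotine Dependence Scale at intake, 3rd trimester, 3 and 6 months postpartum"
- "Depression: Edinburgh Postpartum Depression Scale administered at intake, 3rd trimester, 3 and 6 months postpartum"
- "Anxiety: GAD7 administered at intake, 3rd trimester, 3 and 6 months postpartum"

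The SAP names none of these intake scores as a covariate. Addiction severity does not cover Fagerstrom, because item 8 of the same list ties it to the DSM-5 opioid use disorder criteria.

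The status of the three scales as outcomes is not settled. Aim 2 is to "Evaluate the relative effectiveness of each study arm on primary and secondary maternal and neonatal outcomes", but no list of secondary outcomes follows. The SAP mentions smoking only as a category: "preterm birth, maternal smoking status, etc.) will be summarized with counts and percentages".

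**The concern.** Two things are left open that the design would normally settle.

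- **Stratum.** Sites were randomised within volume strata, so the arms are balanced on volume by construction. If volume is related to the outcome, a model without the stratum counts that difference as noise between sites. The standard error is then too large and the test rejects too rarely. This applies to every outcome, including the noninferiority analysis of neonatal abstinence syndrome (NAS).
- **Intake scores.** For a scale measured before and after, the participant's own intake value is usually the strongest available predictor. Leaving it out loses precision for no saving, since the score is already collected.

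A condition with no trigger and a list with no end also mean that the model can be settled after outcomes by arm are known.

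**Working it through.** The plan gives no figure to reproduce: no alpha, power, margin, ICC or baseline correlation. What follows is illustration.

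**Inputs from the documents**
- Sites: 12 (Study Population, Study Design) or 11 (Research Procedures, Resources).
- Subjects: a maximum of 267 (Short Title Description), read here as women. The Participant Demographics table adds to 15 + 15 + 503 = 533 women, a total that may double count.

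**Assumptions**
- Two-sided 5% level, equal site sizes, continuous score.
- A t reference based on between-site degrees of freedom (df). The SAP names no df method.
- ICC 0.02–0.10 and intake–outcome correlation r of 0.3–0.6.

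**1. Cost of the stratum.** With 12 sites the df fall from 10 to 9 and critical t rises from 2.228 to 2.262: 2.262/2.228 = 1.015. With 11 sites the df fall from 9 to 8: 2.306/2.262 = 1.019. If the strata do not differ, that is the whole effect, an interval 1.5% or 1.9% wider.

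**2. Gain from the stratum when strata differ** (12 sites, 3 per arm per stratum, m = 267/12 = 22.25). The variance of a site mean is s² = ICC + (1 − ICC)/m. A stratum difference of d SD adds 3d²/10 = 0.3d² to the residual variance of the unadjusted model. The CI ratio (adjusted/unadjusted) is therefore 1.015 × √[s²/(s² + 0.3d²)].

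| ICC | s² | CI ratio at d = 0.2 | Break-even d | Type I error without stratum, d = 0.2 (simulated) |
|---|---|---|---|---|
| 0.02 | 0.064 | 0.932 | 0.081 | 3.5% |
| 0.05 | 0.093 | 0.955 | 0.098 | 4.0% |
| 0.10 | 0.140 | 0.974 | 0.120 | 4.2% |

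With the stratum in the model, simulated type I error was 5.0–5.1% (200,000 null trials per setting).

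**3. Intake score plus stratum.** The score is allowed to reduce only within-site variance, and the strata are taken not to differ, so the stratum appears purely as a cost:

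V = [ICC + (1 − ICC)(1 − r²)/m] / [ICC + (1 − ICC)/m]; CI ratio = √V × (t with stratum / t without).

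Example, 267 women, 12 sites, ICC 0.02, r 0.5: V = (0.02 + 0.98 × 0.75/22.25)/(0.02 + 0.98/22.25) = 0.828; √0.828 × 1.015 = 0.924.

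| Women, sites | ICC | r 0.3 | r 0.5 | r 0.6 |
|---|---|---|---|---|
| 267, 12 | 0.02 | 0.983 | 0.924 | 0.881 |
| 267, 12 | 0.05 | 0.994 | 0.955 | 0.927 |
| 267, 12 | 0.10 | 1.002 | 0.978 | 0.961 |
| 267, 11 | 0.02 | 0.988 | 0.930 | 0.888 |
| 267, 11 | 0.05 | 0.999 | 0.962 | 0.935 |
| 267, 11 | 0.10 | 1.007 | 0.984 | 0.969 |
| 533, 12 | 0.02 | 0.991 | 0.946 | 0.914 |
| 533, 12 | 0.05 | 1.001 | 0.977 | 0.959 |
| 533, 12 | 0.10 | 1.008 | 0.994 | 0.984 |

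With 533 women and 11 sites the gains are slightly smaller again. Fewer women per site would raise them.

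**4. What a free choice could do.** If the unadjusted and fully adjusted tests were both run and the better one reported, simulated type I error was 6.1–7.6% over ICC 0.01–0.10 and r 0.3–0.6 (12 sites of 22, no stratum effect). Each test alone held 4.9–5.1%. Most of the excess comes from the intake score; the stratum alone gives 5.5–5.7%.

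**The case against.** The strongest reply is that nothing here is an error. The SAP does not forbid these covariates, a clustered model without them is valid, and with about 12 sites a short model is sensible. That is right as far as it goes. It argues for a short fixed list, though, not for an open one. The intake score varies between participants, so it costs no site-level df.

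Further points stand and limit the claim:
- Nothing designates the three scales as secondary outcomes; that is an inference from their repeated schedule. The Fagerstrom part applies only if its score is analysed as continuous. The stratum argument depends on neither.
- The gain is smaller with 11 sites or more women per site, and every magnitude rests on assumed values. Equal site sizes are assumed although sites are stratified by volume.
- Enrolment runs to 32 weeks and the prenatal collection is at 28–32 weeks (Payment section). For late entrants the intake and third-trimester scores may nearly coincide, so one correlation does not describe that time point.

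A reader might infer that the trial's type I error is inflated to 6–7.6%. The documents do not support that. The wording permits choosing between models but does not plan it, and the four covariates the SAP names were not modelled in that figure.

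**Conclusion.** The point holds as a gap in pre-specification with a concrete better model available. It is worth fixing but not fatal. Leaving out the stratum makes the analysis conservative if the strata differ on the outcome: at an assumed 0.2 SD difference, a nominal 5% test runs at 3.5–4.2% and the interval could be 3–7% narrower. For continuous intake-measured scales at r 0.5–0.6 and ICC 0.02–0.05, the full model narrows the interval by about 4–12% with 267 women and about 2–9% with 533. At ICC 0.10 the corresponding gain is at most about 4%. At r 0.3 it is under 2%, and the interval can be slightly wider.

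Two stronger readings are tempting and fail. The unadjusted test is not invalid: with clustering handled and a suitable reference distribution, omitting these terms does not inflate type I error. Nor is any precision gain from intake scores claimed for NAS, for which only the design argument for the stratum applies; the figures above are for continuous scores. WHO QoL, ECHO and CHSI have no intake measure, so the intake-score argument does not reach them.

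**What to change.** Before outcome data by arm are seen, remove the open-list and conditional wording from the SAP and state one primary model per outcome:
- For every outcome, including the NAS primary analysis: arm, volume stratum and a random site effect.
- For Edinburgh, GAD-7 and Fagerstrom, where analysed as continuous scores: add the participant's own intake score. If smoking is analysed as a category, say so and give its model separately.
- State which of the four named covariates (socioeconomic status, race, age, addiction severity) are kept, and for which outcomes.
- Name the df method.
- Report the unadjusted result as a sensitivity analysis.

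This changes SAP wording only, since the intake scores and strata already exist. The statistical cost is one site-level df under a between-site t reference: an interval about 1.5% wider with 12 sites, or 1.9% with 11, if the strata turn out not to differ.

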**Section 2. Research Involving Neonates**

Research Involving Neonates

**A. Viable Neonates** - A neonate, after delivery, that has been determined to be viable may be included in research only to the extent permitted by and in accordance with the requirement of 45 CFR 46 Subpart A and Subpart D.

Yes  No Does your research involve viable neonates?

If yes, you will need to complete the Children subsection before submitting this application (if the Children subsection is not visible, go to the "Subject Demographics" section, checkmark "Children", and save).

**B. Neonates of Uncertain Viability AND Nonviable Neonates** - Until it has been ascertained whether or not a neonate is viable, a neonate may not be involved in research covered by 45 CFR 46 Subpart B unless the IRB determines that certain conditions are met. Your responses to the following will help the IRB determine whether the conditions are met.

Explain why the proposed research is scientifically appropriate and provide a description of any pre-clinical and clinical studies that have been conducted which provide data for assessing potential risks to neonates.

If not applicable, please enter "N/A".

We will be following up outcomes of neonates of mothers whom we follow through their pregnancies. We will be collecting delivery information, NAS information and collecting developmental outcome data on the infants at 3 and 6 months of life. Our primary outcome is Neonatal Abstinence Syndrome (NAS). We have seen a reduction in NAS at PATHways. NAS is our primary outcome for this study. As such, we will be collecting this data.

Yes  No Will individuals engaged in the research have any part in determining the viability of a neonate?

**C. Neonates of Uncertain Viability - Additional Requirements** - Select the option that applies to your research.

Not Applicable

- The research holds out the prospect of enhancing the probability of survival of the neonate to the point of viability, **AND** any risk is the least possible for achieving that objective.
- The research has the main purpose of the development of important biomedical knowledge, which cannot be obtained by other means **AND** there will be no added risk to the neonate resulting from the research.

Explain the procedures that will be used to obtain legally effective informed consent of either parent of the neonate.

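### The SAP calls for a noninferiority analysis of the primary outcome but fixes no reference arm, direction, margin, scale, confidence level or decision rule, and plans no between-arm interval

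*Combined protocol and SAP*

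**What the plan says.** The SAP is a single paragraph. On the model it says: "To investigate differences in outcomes between treatment arms, a generalized linear mixed model will be performed". On reporting it says: "Results will be presented with means (standard error) by treatment arm". On hypotheses it says: "Note that the primary outcome requires a noninferiority analysis; the secondary outcomes require superiority analysis to identify between-group differences". That last sentence is the only mention of noninferiority in the documents. The SAP also plans descriptive counts and percentages for categorical variables and lists the need for NAS treatment among its examples.

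The protocol's Objectives name two comparisons. Aim 1 is a cluster randomised trial "comparing two delivery modes (local GROUP care vs TELEMEDICINE) for the delivery of a PATHways based patient education curriculum", with neither mode called the reference. Aim 2 is to "Evaluate the relative effectiveness of each study arm on primary and secondary maternal and neonatal outcomes as compared to the established PATHways program" at the University of Kentucky (the Hub). Under Study Design the sites are allocated to the two modes by delivery-volume stratum: "Randomization will be 1:1 within each strata". The Hub is not among the randomised clusters.

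The primary outcome is given simply as NAS in the section on research involving neonates. The neonatal data list under Data Collection & Research Materials gives it as NAS diagnosis together with treatment requirement. The SAP does not say which variable is primary.

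**The concern.** A noninferiority test is directional. It asks whether one named arm is worse than a named reference by less than a stated amount, on a stated scale and at a stated confidence level. Without those elements the label has no operational content. If they are chosen once outcomes by arm are known, the same data can be called noninferior or not, and the type I error of the primary claim has no stated bound.

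The planned output does not fill the gap. A mean and standard error for each arm is not an effect estimate with an interval, and in a stratified cluster design with 11 or 12 sites the between-arm uncertainty has to come from the model, with allowance for the small number of clusters.

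**Working it through.** **1. Search for the required elements.**

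| Element | Where found |
|---|---|
| Comparison | SAP: between treatment arms, generically. Aim 1: GROUP and TELEMEDICINE. Aim 2: each arm and the Hub |
| Reference arm and direction | Nowhere |
| Margin | Nowhere |
| Effect scale | Nowhere |
| Alpha or confidence level | Nowhere |
| Decision rule | Nowhere |
| Between-arm estimate or interval | Not among the planned outputs |

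**2. The plan's own figure.** The only stated sample size is a maximum of 267 subjects, on the application's opening page. No power, margin, event rate, ICC or dropout accompanies it, so it cannot be reproduced or tested.

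**3. Illustration of what the gap can change.** From the documents:
- N = 267
- 12 sites (Study Population, Study Design) or 11 sites (Research Procedures, Resources)
- 1:1 allocation of sites within two volume strata.

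Assumed, not in the documents:
- NAS rate p = 0.3 or 0.5 in both arms
- ICC = 0.01, 0.02, 0.05 or 0.10
- equal site sizes; 11 sites split 6 and 5
- df = sites − 3 (intercept, arm, stratum).

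Formula: SE = √{p(1−p) × [1 + (m−1)ICC] × (1/n₁ + 1/n₂)}, with m = N/sites; half-width = t × SE.

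Worked case, 12 sites, p = 0.5, ICC = 0.05:
- m = 267/12 = 22.25
- design effect = 1 + 21.25 × 0.05 = 2.06
- n₁ = n₂ = 133.5
- SE = √(0.25 × 2.0625 × 2/133.5) = 0.0879
- t(0.975, 9) = 2.262, so the half-width is 19.9 points.

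Two-sided 95% half-widths, in percentage points:

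| Sites | p | ICC 0.01 | 0.02 | 0.05 | 0.10 |
|---|---|---|---|---|---|
| 12 | 0.3 | 14.0 | 15.1 | 18.2 | 22.4 |
| 12 | 0.5 | 15.2 | 16.5 | 19.9 | 24.5 |
| 11 | 0.3 | 14.4 | 15.7 | 19.1 | 23.7 |
| 11 | 0.5 | 15.7 | 17.2 | 20.8 | 25.8 |

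The range is 14.0 to 25.8. If the observed rates are exactly equal, the confidence limit equals the half-width. A 10-point margin then fails in all 16 cells and a 26-point margin passes in all 16.

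**4. Between those margins, other unstated choices matter.** In the worked case:
- two-sided 95%, t with 9 df: 2.262 × 0.0879 = 19.9 points
- two-sided 95%, normal quantile: 1.96 × 0.0879 = 17.2 points
- one-sided 95%, t with 9 df: 1.833 × 0.0879 = 16.1 points.

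An 18-point margin fails under the first and passes under the other two.

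**5. Scale.** A 10-point increase is a risk ratio of 1.50, 1.33 or 1.20, and an odds ratio of 1.71, 1.56 or 1.50, at reference rates of 20%, 30% or 50%. A margin on one scale does not fix a margin on another.

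**The case against.** Several points on the other side stand.

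- **The contrast is not wide open.** A reader might infer that four noninferiority claims fit equally well: either mode against the other, or either against the Hub. The documents do not support equal weight. The SAP speaks of treatment arms, the arms are GROUP and TELEMEDICINE, and the Hub is neither randomised nor called an arm. GROUP against TELEMEDICINE is the natural reading, with direction unstated. Aim 2 covers the primary outcome, so a Hub reading is possible but weaker.
- **The model could supply what is needed.** A mixed model of between-arm differences yields an arm effect and its standard error, and counts and percentages are also planned. It would therefore be too strong to say that a noninferiority conclusion is impossible. The gap is that no effect estimate, interval or rule is prespecified.
- **The margin is not the sole determinant.** Between 14.0 and 25.8 points the NAS rate, ICC and confidence level also decide. The failure of a 10-point margin depends on the assumptions too. At a 20% rate, ICC 0.01 and 12 sites, SE = √(0.16 × 1.2125 × 2/133.5) = 0.0539, and a one-sided 95% limit of 1.833 × 0.0539 = 9.9 points would pass.
- **N might differ.** The planned-enrolment table sums to 15 + 15 + 503 = 533. That is about twice the stated maximum, is not explained, and may count the Latinx row twice, so it is not used here. With 533 the intervals would be narrower.
- **Parts of any remedy are choices.** A risk difference, a two-sided 95% interval and sites − 3 df are defensible, but the documents do not require them.

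None of this supplies a margin, a reference arm or a decision rule.

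**Conclusion.** The concern holds and must be fixed before the primary analysis. The SAP names a noninferiority analysis and leaves out every element that would make it one, and its planned model output cannot be set against a margin. This conclusion rests on the text alone and needs no assumed number.

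The size of the consequence is illustrative. With 267 mothers, 11 or 12 sites and the assumed rates and ICCs, the two-sided 95% half-width of 14.0 to 25.8 points leaves a wide band of margins in which unstated choices settle the verdict.

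Two further inferences should be avoided. The figures do not show that 267 is too small, because no margin or event rate is given against which to judge it. Nor do the documents show that a margin has been or will be chosen after looking at the data; they only fail to prevent it.

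**What to change.** In the SAP:

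1. For the primary outcome, replace the reporting of means and standard errors by arm with a between-arm effect estimate from the generalized linear mixed model. An example is the GROUP versus TELEMEDICINE risk difference, provided the sponsor confirms that this is the intended contrast. Include a random effect for site and a term for the volume stratum used in randomisation. Give a two-sided 95% CI with a small-sample degrees-of-freedom correction for the 11 or 12 clusters.
2. Keep the noninferiority label only if the reference arm, direction, a single NAS endpoint definition and a justified numeric margin on the stated scale are fixed before any outcome is viewed by arm. Declare noninferiority only if the relevant CI limit lies inside that margin. Otherwise, including where outcomes by arm have already been seen, drop the label and report the estimate with its CI.
3. Say whether the Hub was meant as a noninferiority reference, and label any Hub comparison as non-randomised.

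The cost is SAP text only, with no new data. The downside is that the primary claim may be weaker than noninferiority, and the corrected interval is about 15% wider at 12 sites than with a normal quantile (2.262/1.96 = 1.15).
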